3.3.2 Patient population selection criteria

All patients with NSCLC attending participating hospitals during the pre-specified period will be eligible to participate in the study.

Patients will be asked to sign an informed consent form which specifies that there will be no change in clinical management because of the study and that it only involves collecting information[†]

All patients regardless of whether they are participating in clinical trials or not are eligible to be included in the study. This is a purely observational study, therefore participation in this study will not interfere with participation in a clinical trial. The participation in this study will not prevent the patient from being given the opportunity of receiving an investigational product or participating in another study.

A sample of patients (25% of the whole sample) will be asked to complete Quality of Life questionnaires when attending the programmed assessment visits to the physician. Only patients who are not participating in clinical trials will be asked to participate in the Quality of Life sub-study. These patients will be asked to sign a specific informed consent form.

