4.1.3 Patient Reported Outcomes (PROs)

Patient Reported Outcomes play a particular role in this study. They will be measured in a sample (25% of the whole sample) of consenting patients at a limited number of sites per country. The sample will include patients at different stages of the disease during the study period who have received different treatment regimens. It is assumed that there will be a representative sample of advanced stage patients.

Each participating country will endeavour to include patients in the PRO sample bearing in mind that the sample must be representative of the whole study population.

Only patients who are not participating in clinical trials will be asked to participate in the Quality of Life sub-study.

- FACT Questionnaires¹⁹: These are a series of instruments designed to be sensitive to changes in cancer patients. They contain questions designed to measure SWB and EWB as well as PWB and FWB and are simple to use and score. The FACT-L subscale enables the assessment of disease-related symptoms associated with lung cancer.
- EUROQoL/EQ-5D²⁵: This is a standardised instrument for use as a measure of health outcome. Applicable to a wide range of health conditions and treatments, it provides a simple descriptive profile and a single index value for health status.

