6.4 Determination of sample size

The most important aspect when selecting sites is their representativeness in each country. If 80% of NSCLC patients are being managed in large teaching hospitals, then 80% of the study sample should come from this type of hospital. Participating sites should include all the patients meeting inclusion/exclusion criteria during the inclusion period assumed to be 25-30 patients in a 6-months period, since there is no seasonal variability. (Estimated number of new lung cancer patients in large hospitals is 100-125/year).

Since the main objective is to obtain reliable information on how patients are being managed, it is essential to obtain valid information on all therapy lines. For this reason, and bearing in mind the high mortality of the disease, it is very important to have access to a sample large enough to finally provide a core group of patients likely to receive advanced treatment lines (including investigational products), and also to allow comparisons.

Assuming that generally in Central Eastern Europe and Russia 80-85%² of lung cancers are NSCLC, 80-90% of them are diagnosed at phase IIIb/IV (patients most likely to receive several lines of treatment) and of these 75-80% are treated (approximately 33% with investigational products). No published information is available regarding the proportion of these patients who will achieve further treatment lines, but for sample estimation we assumed that no more than 10% of newly diagnosed NSCLC patients would receive an active third line treatment.

It is estimated that approximately 4,000 patients will be included across several Central eastern European countries and Russia. This amount of patients would enable us to obtain a sample of approximately 400 IIIb/IV treated NSCLC patients throughout Europe.

For the descriptive analysis, 600 NSCLC phase IIIB-IV third line patients will allow us to estimate a proportion of 0.5 (taking into account that this is a novel study in NSCLC and the most pessimistic scenario must be considered) with a precision of 0.04, which means estimating 50% with a confidence interval from 46% to 54% (α =0.05).

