It was also considered that the analytical objectives of the study would require multivariate analysis to determine the above sample size. This analysis will consider the main risk variables as independent variables. Based on the formula provided by Freeman²⁶ (the sample size must be 10 times the number of variables plus one) in order to perform such multivariate analysis, and having as variables for comparison: treatment, cycle, phase, primary tumour location, extent of disease, prior surgery, age, sex, EGFR markers, habits, PS/ECOG and type of hospital, the total sample size of 4,000 patients is advised.

Protocol of Non-Interventional Study Drug Substance: N/A

NIS Code: NIS-ORU-IRE-2009/1

Version No: 4.0 Date: 8 December 2009

A sample of 25% of patients per country will be included in the Quality of Life descriptive sub-study. Whether a sample from each site in the study is included in the sub-study will depend on the number of sites participating in each country. The number of sites involved will be determined bearing in mind that 25% of the total population included in the study must be invited to participate in the Quality of Life sub-study.

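### The PRO sample is required to represent the full cohort, yet patients in a clinical trial when invited are barred from it, so that representativeness cannot hold

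*Protocol*

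**What the plan says.** Protocol Section 4.1.3 sets two conditions on the PRO sample in adjacent paragraphs. Countries are to bear in mind that "the sample must be representative of the whole study population". Then: "Only patients who are not participating in clinical trials will be asked to participate in the Quality of Life sub-study". Section 3.3.2 gives the same restriction.

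The main study has no such restriction. Section 3.3.2 states: "All patients regardless of whether they are participating in clinical trials or not are eligible to be included in the study". Section 4.1.2 provides for recording the drugs these patients receive, under a generic research-drug label.

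Section 6.4 sets the size of the sub-study: "A sample of 25% of patients per country will be included in the Quality of Life descriptive sub-study". Its base is everyone included, trial participants among them. The planning assumptions in the same section are that, of the NSCLC patients, "80-90% of them are diagnosed at phase IIIb/IV", and "of these 75-80% are treated (approximately 33% with investigational products".

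**The concern.** A sample can represent a population only if every part of that population can enter it. Here one part is excluded by rule: patients already in a trial when PRO invitations are made. They count in the full cohort, and no section narrows the PRO target population to leave them out.

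The exclusion is unlikely to be neutral. On the Section 6.4 assumptions, investigational treatment occurs among treated stage IIIb/IV patients. Section 6.3 plans to analyse FACT-L and EQ-5D change with attention to differences between treatments, so the barred patients differ from the rest on a factor that the PRO analysis examines. Choosing other sites, enlarging the sample or weighting cannot bring back patients who may not be asked.

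What is at stake is the reach of the quality-of-life results. As written, the protocol lets them be read as describing the whole cohort, when they can describe only patients who were outside trials at invitation.

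**Working it through.** **The contradiction needs no arithmetic.** Call the study population S and the patients in a trial at invitation T. Section 3.3.2 places T inside S. Section 4.1.3 requires the PRO sample to represent S, and both sections prevent anyone in T from being asked. Unless T is empty, the requirement fails. Section 6.4 expects investigational products to be in use, so the plan does not treat T as empty.

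**Size.** The protocol gives no figure for T, so there is none to reproduce. An illustration can be built from Section 6.4, on the assumption that every use of an investigational product is trial participation already under way at invitation.

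Inputs, all from Section 6.4: stage IIIb/IV 0.80-0.90; treated, given IIIb/IV, 0.75-0.80; on investigational products, given treated, about 0.33.

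Share = P(IIIb/IV) × P(treated) × P(investigational)

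- Low: 0.80 × 0.75 × 0.33 = 0.198
- High: 0.90 × 0.80 × 0.33 = 0.238
- Of the 4,000 planned overall: 792 to 950
- Of the 500 planned in Russia (protocol summary): 99 to 119

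If the 33% is instead read as a share of all IIIb/IV patients, the result is 0.80 × 0.33 = 0.264 to 0.90 × 0.33 = 0.297.

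**Effect on composition, same assumption.** Treated IIIb/IV patients make up 0.80 × 0.75 = 60% to 0.90 × 0.80 = 72% of the cohort. Among those who may be asked, they make up (0.60 − 0.198)/(1 − 0.198) = 50% to (0.72 − 0.238)/(1 − 0.238) = 63%. Across the four combinations of the ranges, the overall IIIb/IV share moves less, from 80-90% to about 75-87%.

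**Effect on sampling, same assumption.** Filling a sample of 25% of everyone from those who may be asked means taking 0.25/(1 − 0.198) = 31% to 0.25/(1 − 0.238) = 33% of them. The documents do not show that this rate is a problem.

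**How timing changes the share.** The bar applies when patients are invited. The protocol summary has questionnaires collected straight after consent, Section 3.1 starts PROs at the first visit, and Table 1 marks them at inclusion. The 33% has no time point, and Section 6.4 also mentions investigational products in connection with advanced treatment lines. If only a fraction f of these patients are in a trial at invitation, the excluded share is f × 19.8% to f × 23.8%, and the documents do not give f. In the other direction, trials in non-advanced patients, or without an investigational product, would add to the share and are not counted above.

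**The case against.** The strongest reply is that the bar is open, probably deliberate and only loosely in conflict with an aim. Section 4.1.3 says that countries will endeavour to meet the requirement, Section 6.4 calls the sub-study descriptive, and no section says that quality-of-life results will be presented as describing the whole cohort. This softens the point but does not remove it. The aim is still worded as something the sample must satisfy, and no country can satisfy it.

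A reader might go further and infer that the protocol's own figures put about a fifth of all patients beyond reach, with no chance of entering the PRO sample. The documents do not support that. Someone who joins a trial at second or third line may already be in the sample: Section 3.3.2 says that the study does not stop patients joining another study, and Section 3.3.3.1 lists no PRO withdrawal criterion for trial entry. Only patients in a trial when asked have no chance of selection, and their number is not given.

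A reader might also infer that the barred patients are a group whose quality of life the plan singles out. Section 6.3 attaches special interest to change scores in FACT-L and EQ-5D, not to a group of patients.

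Finally, a baseline comparison table is ordinary SAP content. Its absence from the protocol is no fault. It is offered below only as part of the remedy.

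**Conclusion.** The point holds as a contradiction about the target population. A sample that bars patients in a trial at invitation cannot represent a cohort that includes them. Target population and eligibility are protocol matters, and here the protocol states both in terms that do not fit together.

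The size is uncertain. About 20-24% is an illustration that equates all investigational-product use in Section 6.4 with trial participation at entry. The true share could be lower because of later trial entry, or higher because of trials outside that calculation. The percentages are planning assumptions, not data. The conclusion depends only on the share not being zero.

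The exclusion itself is not shown to be wrong, and nothing here affects the main cohort. What needs correcting is the claim made for the PRO sample.

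**What to change.** Keep the exclusion, and keep the sample at 25% of the whole study. In Sections 4.1.3 and 6.4, restate the PRO target population along these lines: *The PRO sample should be representative of study patients who are not participating in a clinical trial when they are invited, and quality-of-life conclusions apply to these patients.* Align Section 3.3.2 so that it too refers to trial status at invitation.

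Add one table of baseline stage, performance status, age and treatment for three groups: PRO patients, other patients not in a trial, and trial patients. Sections 4.1.1 and 4.1.2 already provide for collecting these items. Trial participation is not named there as a variable. If the case report form has no field for it, the research-drug entries with their start dates identify trial patients approximately and would miss trials without a study drug.

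The 25% should not be rebased to non-trial patients. On the illustrative figures, that would give 0.25 × (1 − 0.238) = 19% to 0.25 × (1 − 0.198) = 20% of the total, or about 760-800 instead of 1,000 of 4,000. That would lose about a fifth of the PRO sample for no gain on this point.

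The cost is a narrower quality-of-life claim and one extra table. No visits or questionnaires are added.

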4.2 Screening and demographic measurements

Each site will be responsible for maintaining an updated record of the number of patients who are included or not included in this study. An explanation of why patients were not included must be available.

4.3 Measurement of Outcomes Variables

4.3.1 Administration of Patient-Reported Outcomes (PRO)

The PRO questionnaires are self-administered and the patients will be asked to complete them at each evaluation visit. Evaluation visits are those in which an assessment of a procedure (once the responsible clinician of treating this type of patients has the results of such

Version No: 4.0 Date: 8 December 2009

procedure, and NOT at the time of the visit performing the procedure), or any other tumour evaluation is made by this person.

Appropriate procedures to minimise bias and enhance compliance will be followed throughout the study. The patient will complete the questionnaires independently, so that the answers reflect the patient's perceptions and views. Optimally, the questionnaires will be completed prior to patient-physician interview, before there are substantial professional encounters with transmission of information, such as disease status. Such information may influence the answers the patients provide on questionnaires. Information to the patients on how to complete the questionnaires is provided in the questionnaires.

It is recommended that, following completion of the questionnaires, the investigators perform the clinical evaluation. Before the patient leaves the clinic, the investigator, once the clinical evaluation is finished, should review the patient questionnaires to avoid any uncompleted responses.

The methods for collecting Patient Reported Outcomes (PRO) data are presented below.

4.4 Safety reporting

Due to the non-interventional character of a Non-Interventional Study, no pro-active safety data collection should take place. Only spontaneously mentioned safety events should be reported as required by the post-marketing pharmacovigilance regulations.

4.4.1 Definitions

The definition of an adverse drug reaction (ADR) is given below. It is of the utmost importance that all staff involved in the study is familiar with the content of this section. The investigator is responsible for ensuring this.

Adverse Drug Reaction (ADR)

An ADR is the development of an undesirable medical condition or the deterioration of a preexisting medical condition following or during exposure to a medicinal product, suspected to be causally related to the product.

5. DATA MANAGEMENT

5.1 Collection, monitoring and processing of data

An electronic case report form (eCRF) and also a paper case report form (pCRF) will be provided to all participating countries that have been designated to answer all of the proposed variables. Each local study coordinator will be responsible for providing this eCRF/pCRF to each participating site in time for them to start the study on time according to the timelines described in this protocol.

Protocol of Non-Interventional Study Drug Substance: N/A

NIS Code: NIS-ORU-IRE-2009/1

Version No: 4.0 Date: 8 December 2009

Data will be collected from the medical record of each patient at the time of each evaluation visit. At this time the investigator or the person responsible for recording the data will enter information into the eCRF/pCRF regarding the current visit and any relevant information regarding intermediate visits (from the previous one to the current one) of the patient to the department responsible of treating this type of patients.

Data entered into the eCRF, once saved, will be automatically transferred to the core Data Management Office, where all the information will be tabulated.

Although the source data will not be verified in this study, the eCRF will have a set of data checks in order to avoid inconsistencies. Data will not be monitored in this study, but queries could arise from the person responsible for Data Management.

Furthermore, in order to make data collection easier, the eCRF will provide an instruction manual on how to complete each of the variables, as well as examples for each of them.

There will be NO possibility of adapting or changing data or adding any data to those collected for entry into the eCRF.

The following will be globally organized and managed by the AstraZeneca Lung-EPICLIN Coordination Office:

- Development/adaptation of pCRFs and questionnaires.
- Minimum quality assurance requirements.
- Data management.
- Data analysis as described below.

Each country will decide if data is to be collected by a CRO or by hospital personnel.

The following will be locally organized and managed by the local study coordinator:

- All aspects of local data collection.
- Provide information and support to the investigator(s) on data collection.
- Quality assurance. Ensure that minimum quality requirements described in this protocol are met locally.

Version No: 4.0 Date: 8 December 2009

6. STATISTICAL METHODS AND DETERMINATION OF SAMPLE SIZE

6.1 Statistical evaluation – general aspects

All statistical analysis will be performed by the AstraZeneca Lung-EPICLIN Coordination Office and ALMEDIS CRO by means of the SAS® statistical software system.

The two-sided 95% confidence interval will be obtained for the population estimation of the variables

A comprehensive Statistical Analysis Plan (SAP) will be prepared before database lock.

6.2 Analysis of outcome variables in relation to objectives and hypotheses

Three groups will be created from baseline evaluation for the purpose of data analysis. The patients will be divided according to the baseline stage of their disease (non-advanced NSCLC patients, locally advanced NSCLC patients and metastatic NSCLC patients). For each of them the following variables will be considered:

- Clinical evolution from baseline to each visit:
 - o Changes in number of disease-related symptoms.
 - o Changes in the extent of the disease.
- Treatment response from baseline to each visit:
 - o Number of patients with complete response to treatment.
 - Number of patients with partial response to treatment.
 - Number of patients with stable disease under treatment.
 - o Number of patients with progression of disease after treatment.
 - O Progression-free time from the last progression or diagnosis to new progression of disease during the study period. The main analysis of the time to disease progression will be a Cox proportional hazards model to estimate the hazard ratio of progression among the analysis groups, with 95% confidence intervals. This will be a 2-sided test of the hypothesis, with a statistical significance level of 0.05. The assigned treatment will be included as a covariate.
- Treatment-related events.

Protocol of Non-Interventional Study

Drug Substance: N/A

NIS Code: NIS-ORU-IRE-2009/1

Version No: 4.0 Date: 8 December 2009

> o Mean number of patients with any treatment related event during the study period.

> o Mean number of patients with any serious treatment related event during the study period.

Mortality.

- o Number of patients with documented death during the study period.
- o Number of patients with a documented death due to NSCLC during the study period.

6.3 Method of statistical analysis

Considering the study objectives, the analysis strategy will be as follows:

A descriptive analysis approach will be used to analyse NSCLC population, clinical management, clinical outcomes and health care resources.

Descriptive statistics will include frequency tables (n, mean, median, standard deviation, minimum and maximum for continuous variables and n, frequency and percentage for categorical values).

The assessment of different associations will be as follows:

Logistic and general linear models (GLM) will be used to assess the association of patient characteristics (including stage of disease, histology, PS, etc) and clinical management (independent variable) with clinical outcome variables (clinical evolution, treatment related events, mortality). The interest will separately focus on the treatment differences between each of them or a group of them used. Model-based point estimates of odds ratios and corresponding 95% confidence intervals will be reported (when applicable). P-values will be reported for comparisons between different treatments.

A descriptive analysis approach will be used to assess factors related with the use of health care resources, and a comparison of the level of use of health care resources will also be made.

The assessment of quality of life will be as follows:

Changes in FACT-L total score from first visit to the visit prior to a specific treatment response with focus on treatment differences. This is a variable of particular interest and will be analysed using an ANCOVA model.

Changes in FACT-L total score from first visit to each assessment will be analysed using an ANCOVA model.

Version No: 4.0 Date: 8 December 2009

Changes in EQ-5D total score from first visit to the visit prior to a specific treatment response with focus on the differences between treatments. This is a variable of particular interest and will be analysed using an ANCOVA model.

Changes in EQ-5D total score from first visit to each assessment will be analysed using an ANCOVA model.

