All NSCLC patients attending the responsible department of treating this type of patients (e.g. Oncology Department, Pulmonology Department) for the first time (regardless of whether the patient is diagnosed with locally, advanced or metastatic disease) at the participating sites

Version No: 4.0 Date: 8 December 2009

from the first of January 2010 to the end of July 2010. Patients diagnosed, or even treated, in other departments within the same hospital or in another hospital are susceptible to be included in the study if full access to the patient's medical record is made available.

Methods

The inclusion period will last 6 months, from the 1st of February 2010 to the 1st of August 2010. All patients attending the responsible department of treating this type of patients for the first time during this period should be included in the study. Patients could be retrospectively included in case of not receiving the Ethics Committee approval by the first of January 2010, but only those patients attending for the first time during the enrolment period.

The follow-up period will last for at least one year (the follow-up period will be conducted until the end of July 2011, so the maximum follow-up period will comprise 18 months) or until the patient is deceased, lost to follow-up or changed to another hospital.

Information regarding patients and disease characteristics as well as clinical management approach (diagnostic methods, treatments and follow-up patterns) and final outcomes will be taken from the medical record at each evaluation visit. These visits will be performed according to normal clinical practice.

Functional status and Quality of Life (QoL) questionnaires will be collected directly from the patients immediately after obtaining informed consent.

All patients regardless of whether they are participating in clinical trials or not are eligible to be included in the study. This is a purely observational study, therefore participation in this study will not interfere with participation in a clinical trial.

Statistical Analysis

A descriptive analysis approach will be used to analyse NSCLC population, clinical management, clinical outcomes and use of health care resources.

Version No: 4.0 Date: 8 December 2009

TABLE OF CONTENTS

PAGE

SUMMA	RY OF THE NON-INTERVENTIONAL STUDY PROTOCOL	2
TABLE (OF CONTENTS	8
LIST OF	ABBREVIATIONS AND DEFINITION OF TERMS	11
1.	INTRODUCTION	13
1.1	Background and rationale	13

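### Mortality is modelled as a yes/no outcome although follow-up varies from 12 to 18 months and stops at transfer or loss, so the odds ratios have no common time horizon

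*Protocol*

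**What the plan says.** Section 6.2 lists under mortality "Number of patients with documented death during the study period", and the same count restricted to deaths from NSCLC. It gives no time origin, horizon or censoring rule for either.

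Section 6.3 then states: "Logistic and general linear models (GLM) will be used to assess the association of patient characteristics". The sentence goes on to a second set of explanatory variables and names the outcomes: "clinical management (independent variable) with clinical outcome variables (clinical evolution, treatment related events, mortality"). For the effect measure, the section says "Model-based point estimates of odds ratios and corresponding 95% confidence intervals will be reported (when applicable"). On testing, it says "P-values will be reported for comparisons between different treatments".

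The Methods part of the Protocol summary sets follow-up at one year or more, with 31 July 2011 as the common closing date: "so the maximum follow-up period will comprise 18 months) or until the patient is deceased, lost to follow-up or changed to another hospital". Time-to-event analysis appears only in Section 6.2, where progression is given a Cox model.

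The sample-size argument in Section 6.4 names the variables intended for multivariate analysis: "treatment, cycle, phase, primary tumour location, extent of disease, prior surgery, age, sex, EGFR markers, habits, PS/ECOG and type of hospital". It does not say how treatment or cycle would be coded, or for which outcome.

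**The concern.** A yes/no death variable treats a patient watched for 12 months, one watched for 18 months and one who moved hospital at month four as equally observed. A patient who transfers and dies elsewhere has no documented death and, on a plain reading, counts as a survivor. A group that entered earlier shows more deaths, and a group that transfers more often shows fewer, at the same underlying risk.

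A second problem depends on what enters the model. Later lines and cycle counts become known only once the patient has lived long enough to receive them. A logistic model has no time axis and can take such a variable only as one fixed value per patient, which makes longer survival look like a benefit of therapy.

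The comparisons at stake are among the stated objectives. Section 2.1.2 asks for outcome differences among countries and for factors associated with outcome. Section 3.2 looks to comparisons among treatments and countries, and Section 6.4 calls valid information on all lines of therapy essential.

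**Working it through.** **1. The follow-up range.** To 31 July 2011, entry on 1 February 2010 gives 17.9 months and entry on 1 August 2010 gives 12.0. This reproduces the stated 12 to 18 months. (Section 3.3.2.1 opens eligibility on 1 January 2010, which would give 18.9 months; the two start dates need reconciling.)

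**2. Hazard.** Section 1.1 gives one-year survival of 35% and median survival of 7-10 months for stage IIIB/IV disease on first-line chemotherapy. Assuming a constant hazard, h = -ln(0.35)/12 = 0.0875 per month. The implied median is ln(2)/h = 7.9 months, inside the stated range.

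**3. Extreme entry dates.**
- Death by 12 months: 1 - exp(-12h) = 0.650.
- Death by 18 months: 1 - exp(-18h) = 0.793.
- Odds ratio: (0.793/0.207)/(0.650/0.350) = 2.06. Medians of 10 and 7 months give 1.91 and 2.17.

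**4. A site that starts late and does not back-fill.** Assume entry uniform over the site's open period. Average death probability for follow-up spread evenly from 12 to b months is 1 - [exp(-12h) - exp(-bh)]/[(b - 12)h].
- On time, b = 18: 1 - (0.3500 - 0.2071)/0.5249 = 0.728, odds 2.672.
- Two months late, b = 16: 1 - (0.3500 - 0.2467)/0.3499 = 0.705, odds 2.386. On-time against late: 1.12 (1.11 to 1.13 for medians of 10 to 7 months).
- Four months late, b = 14: 0.679, odds 2.114. On-time against late: 1.26 (1.24 to 1.28).

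**5. Transfer.** The Protocol gives no transfer rate, so assume a proportion a per year, unrelated to risk, with m = -ln(1 - a)/12. Documented death is the average over follow-up F from 12 to 18 months of [h/(h + m)] × [1 - exp(-(h + m)F)].

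| Transfer per year (assumed) | Documented death | Odds ratio against none |
|---|---|---|
| 0% | 72.8% | 1.00 |
| 10% | 69.1% | 0.84 |
| 20% | 65.4% | 0.71 |
| 30% | 61.5% | 0.60 |

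**6. Therapy begun after entry, no true effect.** Assume a fraction q would receive it at month s if still alive. Write p = 0.728 for overall death.
- Recipients: q × exp(-hs) of the cohort, with death probability 1 - (1 - p) × exp(hs).
- For q = 0.6 and s = 6: 0.6 × 0.592 = 0.355 receive it. Their death probability is 1 - 0.2723 × 1.690 = 0.540. For the rest it is (0.7277 - 0.355 × 0.540)/0.645 = 0.831. The odds ratio is (0.540/0.460)/(0.831/0.169) = 0.24.
- s = 4 gives 0.37 and s = 8 gives 0.15. Reaching a fourth cycle at week 9 (q = 0.7) gives 0.50.

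**7. The same scenarios analysed over time.** In a null simulation of two million patients, deaths per person-time, with censoring at transfer and time-dependent treatment status, gave rate ratios of 1.00 for every transfer rate and every later-line start above.

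**The case against.** Several points on the other side stand, and they limit the claim.

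- **The 2.06 is not a bias in any planned estimate.** It sets a first-day entrant against a last-day entrant. A covariate's odds ratio is distorted only if entry date, transfer or loss differs by that covariate; otherwise it merely lacks a defined horizon.
- **Late-opening sites may not look better.** Section 3.1 allows retrospective inclusion where ethics approval is late, for patients first seen within the enrolment period. That softens step 4. It does nothing for transfer or loss.
- **The 35% belongs to stage IIIB/IV disease**, while all stages are enrolled. With assumed medians of 24 and 36 months, the extreme contrast is still 1.65 and 1.59.
- **The coding of transferred patients is not stated in Section 6.3.** Excluding them would not help. At 20% transfer a year, 65.4% have a documented death and 20.7% reach the end of follow-up alive. The death proportion becomes 0.654/(0.654 + 0.207) = 0.760 against 0.728, an odds ratio of 1.18, now biased the other way.
- **A SAP is promised before database lock** and could hold coding and censoring detail. But the Protocol itself names the model family and effect measure for mortality, and reserves Cox regression for progression. That is a stated choice.

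A reader might infer that the plan puts treatment and cycle into the mortality model as fixed covariates. The text does not say so. The list in Section 6.4 supports a sample-size rule of thumb and is not tied to mortality. Section 6.3 promises p-values between treatments, not between line numbers or cycle counts.

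**Conclusion.** The concern holds for the death analysis as written: a count of documented deaths, modelled by logistic regression over unequal and truncated follow-up, gives odds ratios without a common horizon. They are biased where entry date, transfer or loss differs by country, site or treatment. Plausible sizes are 1.12 to 1.26 for a start two to four months late without back-filling, and 0.84 to 0.60 for transfer of 10% to 30% a year against none. The 2.06 is an outer bound from the extreme entry dates.

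Immortal time is a conditional consequence. If later lines or cycle counts enter these models, the illustrative odds ratios under no effect are 0.15 to 0.50. Treatment fixed at entry is not affected.

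All sizes assume a constant hazard at the stage IIIB/IV rate and uniform entry. Transfer rates, treatment timings and the fractions treated are assumptions, as the Protocol gives none.

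**What to change.** Amend Sections 6.2 and 6.3 as follows.

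- Analyse death as time from a defined origin, such as study entry. Report Kaplan-Meier curves with 12-month survival and fit Cox models, censoring at transfer, loss or end of study.
- Add a sensitivity analysis for informative transfer or loss, since patients who move or disappear may differ in risk.
- Enter therapy begun after entry, line and cycles as time-dependent covariates or by landmark. A Cox model with ever-treated coding would keep the immortal-time bias.
- Keep logistic models only for outcomes assessed over a common window; 12 months is available by design.
- Confirm that the eCRF termination module records date of death and date of last contact. Section 4.1.1 lists death by cause and names neither date; visit and therapy dates are already listed in Section 4.1.2. This should be settled before data collection, because a later SAP cannot supply dates that were not collected.

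The cost is revised wording, a little more programming and possibly two date fields.
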